### 8.1.3.2 Haemostatic response during surgery

**Table 8-2 Haemostatic response during surgery**

Category	Definition
Excellent	blood loss less than expected
Good	blood loss as expected
Moderate	blood loss more than expected
None	uncontrolled bleeding

This evaluation must be performed by the surgeon and the investigator should ensure to document it in the eCRF.

### 8.1.3.3 Surgery visit

Surgery must be performed at a dedicated surgery visit. See Section [1.2](#) for procedures and assessments to be performed during a surgery visit.

## 8.2 Safety assessments

Planned time points for all safety assessments are provided in Section [1.2](#).

A **concomitant illness** is any illness that is already present at the time point from which AEs are collected or found as a result of a screening procedure or other trial procedures performed before exposure to trial product.

**Medical history** is a medical event that the patient experienced prior to the time point from which AEs are collected.

In case of an abnormal and clinically significant finding fulfilling the definition of a concomitant illness or medical history, the investigator must record the finding on the Medical History/Concomitant Illness form.

### 8.2.1 Physical examinations

The physical examinations will be performed according to local procedure and will include:

- General appearance
- Ears, eyes, nose, throat and neck
- Respiratory system
- Cardiovascular system
- Gastrointestinal system, including mouth
- Musculoskeletal system
- Central and peripheral nervous system (general evaluation)
- Skin
- Lymph node palpation

Target joints: Patients will be asked about number and location of target joints. Target joints are defined as 3 or more bleeding episodes in the same joint within 6 months.

Any changes in the examination between the visits which fulfil the criteria of an AE must be recorded as such (see [Appendix 3](#) in Section [10.3](#)).

Clinically significant findings present at screening must be documented as concomitant illness and during the trial as AEs.

Investigators should pay special attention to clinical signs related to previous serious illnesses.

## Body weight

Body weight will be measured in kilos (kg) with one decimal without shoes and wearing only light clothing. Body weight should be measured preferably at the same time of the day and by using the same calibrated scale throughout the trial, if possible.

## Height

Height is measured without shoes in centimetres or inches and recorded in the eCRF to nearest  $\frac{1}{2}$  cm or  $\frac{1}{4}$  inch.

## Body Mass Index

Body mass index will be calculated by the investigator at the screening visit 1 and documented in the subject medical record.

### 8.2.1.1 Neurological examination

The following neurological examinations will be performed by the investigator (haematologist) or an appropriately trained designee under their supervision upon the outline specified in [Appendix 6](#) (this outline has been developed with guidance from a neurologist):

- General neurology including level of consciousness
- Cranial nerves in relation to sight including reaction to light, visual fields and acuity, and eye movements, facial sensation and movement, hearing, palate sound and tongue movement, and trapezius muscle function
- Tone of upper and lower extremity right and left
- Strength of upper and lower extremity right and left
- Reflexes of the biceps, triceps, knee and ankle right and left
- Sensory aspect of cold, pin prick, light touch and proprioception (toe up/down)
- Gait with regards to walking, running, on heels and toes, tandem (toe/heel walk), stand/hop on one leg/foot right and left, and Romberg sign
- Coordination and Fine Motor including finger-to-nose, rapid index finger tap and rapid finger movement right and left

If a patient have not had a specific neurological examination at baseline (visit 2a) then that examination item should not be performed during subsequent visits as per flowchart [Table 1-1](#).

### 8.2.2 Vital signs

Before measurement of vital signs the patient must rest comfortably for at least three minutes and all measurements should, if possible, be performed using the same method and position (e.g. sitting or lying down) throughout the trial for each individual patient.

Vitals signs include assessment of:

- Body temperature (according to local standard practice)
- Pulse
- Blood pressure
- Respiratory rate (resp./min)

Elevated BP is defined as a systolic BP >160 mmHg or a diastolic BP >95 mmHg. Decreased BP is defined as a systolic BP <90 mmHg or a decrease from pre-dose of more than 30 mmHg.

Results of vital signs must be reported in the eCRF. Clinically significant findings present at screening must be documented as concomitant illness and during the trial as AEs.

### 8.2.3      **Electrocardiograms**

12-lead ECG will be obtained at the screening visit and at the end of treatment visit. For the ECG recording, the patients must be resting and in a horizontal position. Any irregularities observed during the ECG, e.g. cough, should either induce a re-run of the ECG and/or be annotated in the eCRF page with description of the occurrence. Printouts must include date, time, patient's identification, and initials of the investigator, and at least 2 complexes for each lead and a single rhythm strip of 6 beats. Electronic capture of these measurements may also be performed.

The evaluation should be made by the investigator or delegated to a cardiologist.

Results of the ECG recording must be reported in the eCRF. Clinically significant findings present at screening must be documented as concomitant illness.

### 8.2.4      **Clinical safety laboratory assessments**

All protocol-required laboratory assessments, as defined in [Appendix 2](#), must be conducted in accordance with the laboratory manual and Section [1.2](#)). An investigator must sign, date and categorise the laboratory results. Categorisation will be either "normal", "out of normal range, not clinically significant" or "out of normal range, clinically significant". Clinically significant findings at Visits 1 and 2a must be recorded as Concomitant Illness, while clinically significant findings from Visit 2b until Visit 7 (included) must be recorded as AEs. Abnormalities should only be recorded as AEs if not present or worsened from baseline/previous assessments. Laboratory results are considered as source data and must be signed and dated by the investigator to verify that the data has been reviewed and that any AEs have been reported.

The administration of N8-GP will be performed after collection of all blood samples for the laboratory tests, except the recovery samples which must be collected 30 minutes after administration of N8-GP.

### 8.3 Adverse events and serious adverse events

The investigator is responsible for detecting, documenting, recording and following up on events that meet the definition of an AE or SAE.

The definition of AEs and SAEs can be found in [Appendix 3](#), along with a description of AEs requiring additional data collection.

Some AEs require additional data collection on a specific event form. This always includes medication error, misuse and abuse of IMP. The relevant events, together with AESIs, are listed in [Table 8-3](#).

**Table 8-3 AEs requiring additional data collection (serious and non-serious AEs) and AESIs**

Event type	AE requiring additional data collection	AESIs
Medication error	X	
Misuse and abuse	X	
Hypersensitivity	X	
FVIII inhibitors		X
CNS-related AEs		X
Renal or hepatic AEs		X
Thromboembolic events		X

A detailed description of the events mentioned in the above table can be found in [Appendix 3](#).

#### 8.3.1 Time period and frequency for collecting AE and SAE information

All AEs and SAEs must be collected from the first administration of trial product at Visit 2a and until the end of the trial (follow-up visit) at the time points specified in the flowchart in Section [1.2](#).

Medical occurrences that take place or have onset prior to the time point from which AEs are collected will be recorded as concomitant illness/medical history. AE and SAE reporting timelines can be found in [Appendix 3](#). All SAEs must be recorded and reported to Novo Nordisk or designee within 24 hours, and the investigator must submit any updated SAE data to Novo Nordisk within 24 hours of it being available.

Investigators are not obligated to actively seek for AE or SAE in former trial patients. However, if the investigator learns of any SAE, including a death, at any time after a patient has been discontinued from/completed the trial, and the investigator considers the event to be possibly/probably related to the trial product or related to trial participation, the investigator must promptly notify Novo Nordisk.

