Protocol  
Trial ID: NN7088-4595Date: 05 July 2021 | Status: Final  
Version: 4.0 | Page: 16 of 102 | Novo Nordisk

	Protocol Sections	Screening	Baseline a, b	Treatment period					End of treatment	Discontinuation of treatment	End of trial (Follow up)	Surgery
Visit		V1	V2a	V2b	V3	V4	V5	V6	V7	V7a	P8	
Timing of Visit (Weeks)		-2	0		4 days after visit 2a	4	8	12	20	28	30D	
Visit Window (Days)		-7	0		0	±7	±7	±7	±7		+5	
HIV d	10.2	X										
Factor VIII Inhibitor in Plasma	10.2.8.6.1	X e	X e		X f	X f	X f	X f	X f	X f		
Anti-N8-GP antibodies	8.6.2	X	X		X	X	X	X	X	X	X	
Anti-PEG antibodies	8.6.3		X							X	X	
Anti-HCP antibodies	8.6.4		X							X g		
PK b	1.2.8.5		X e							X		
Administration of Trial Product	4.1.1		X		X	X	X	X	X		X	
Drug Dispensing	6.2		X		X	X	X	X	X		X	
Dispensing Visit	6.2		X		X	X	X	X	X		X	
Drug Accountability	6.2, 6.4		X		X	X	X	X	X		X	

Protocol  
Trial ID: NN7088-4595Date: 05 July 2021 | Status: Final  
Version: 4.0 | Page: 17 of 102

	Protocol Sections	Screening	Baseline a, b	Treatment period					End of treatment	Discontinuation of treatment	End of trial (Follow up)	Surgery
Visit	V1	V2a	V2b	V3	V4	V5	V6	V7	V7a	V7	P8	
Timing of Visit (Weeks)	-2	0		4 days after visit 2a	4	8	12	20	28		30D	
Visit Window (Days)	-7	0	0	±7	±7	±7	±7	±7	±7		+5	
IWRS session	6.2 , 6.3	X	X	X	X	X	X	X	X			
Hand Out and Instruct in Diary	8.7			X	X	X	X	X	X			
Home treatment training	8.8			X								
Training in Devices	8.8			X								

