#### Footnotes

- a All screening assessments must be completed and evaluated by the investigator before the patient can be included in the trial.
- b Refer to [Table -1](#) for patients that will participate in PK assessments
- c To be measured pre-injection and 30 min (± 10min) post-injection.
- d If positive HIV test, then a HIV polymerase chain reaction (PCR) viral load assessment should be performed
- e Time from last treatment with current FVIII product should be at least 96 hours. The blood sample should be taken before any injection of N8-GP, if applicable.
- f Time from last treatment with N8-GP should be at least 96 hours. The blood sample should be taken before any injection of N8-GP, if applicable.
- g Only to be assessed in case of an acute, severe allergic/anaphylactic reaction.
- h Neurological assessments should not be performed for the assessments not performed at baseline (visit 2a).

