#### 4.1.6 Treatment during screening and follow-up periods

Patients should follow their normal treatment regimen during the screening and follow-up periods. Treatments will not be reimbursed by Novo Nordisk during these periods. Bleeds that occur during the screening and follow-up periods should be treated as per standard local practice and will not be assessed.

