### 5.4 Screen failures

Screen failures are defined as patients who consent to participate in the clinical trial but are not eligible for participation according to in/exclusion criteria. A minimal set of screen failure information is required to ensure transparent reporting of screen failure patients to meet requirements from regulatory authorities. Minimal information includes demography, screen failure details, eligibility criteria, and laboratory results. A screen failure session must be made in the interactive web response system (IWRS).

Individuals who do not meet the criteria for participation in this trial may not be rescreened. Resampling is not allowed if the patient has failed one of the inclusion criteria or fulfilled one of the

exclusion criteria related to laboratory parameters. However, in case of technical issues (e.g. haemolysed or lost), re-sampling is allowed for the affected parameters.

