### 6.5.1 Prohibited Medication

The following medications are **not** allowed during the course of the trial until after the End of Treatment visit.

- Bypassing products: activated recombinant factor VII (rFVIIa), plasma-derived prothrombin complex concentrates (pd-PCC) and plasma-derived activated prothrombin complex concentrates (pd-aPCC).
- Coagulation Factors: FVIII, FIX and FVII-containing products other than N8-GP and other FVIII-containing products like fresh frozen plasma or cryoprecipitate (exception: current FVIII is allowed until 96 hours before Visit 2a).
- Anti-coagulants such as Heparin and vitamin-K antagonists. Heparin is allowed for sealing of central venous access devices according to local practice.

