## 8.5 Pharmacokinetics

Patients will be administered a single i.v. bolus injection of 50 IU/kg of N8-GP at Visit 2a and at Visit 7. The PK sessions extends over 96 hours. Overnight stay is not required. After completion of the PK sessions the patients will return to prophylaxis treatment with the next visit in line.

Patients must not have received current FVIII product for at least 4 days (96 hours) prior to the administration of trial product for the single-dose PK session at visit 2a, (i.e., a wash-out period of at least 96 hours must be applied before visit 2a).

There is no wash-out period for the steady-state PK session at visit 7, however administration of trial product at visit 7 should be approximately 96 hours after the previous N8-GP dose.

Patients must not be actively bleeding during the pharmacokinetic sessions.

The lines/tubes must be flushed immediately after administration of the trial product.

The pharmacokinetic endpoints (see Section [3.2.2.3](#)) will be based on assessments performed from 1 hour prior to and up to 96 hours after administration of N8-GP at Visit 2a (single-dose PK assessments) and Visit 7 (steady-state PK assessments) (see flowchart for PK assessments in Section [1.2](#)).

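### Serious events caused by the mandated 96-hour FVIII-free interval before visit 2a fall outside AE/SAE collection and trigger no 24-hour report to the sponsor

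*Protocol*

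**What the plan says.** **Start of safety collection.** Protocol 8.3.1: "All AEs and SAEs must be collected from the first administration of trial product at Visit 2a". For anything earlier, the same section says: "Medical occurrences that take place or have onset prior to the time point from which AEs are collected will be recorded as concomitant illness/medical history". The AE row of the flowchart (1.2) also begins at visit 2a, and SAP 5.4.2.2 tabulates only events after dosing.

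**The FVIII-free interval.** Protocol 6.5.1 prohibits other FVIII products, with one allowance: "exception: current FVIII is allowed until 96 hours before Visit 2a". Sections 4.1.4, 7.1 (criterion 6) and 8.1.1 repeat this limit for all patients. For patients in the PK sessions, section 8.5 calls it a wash-out: "a wash-out period of at least 96 hours must be applied before visit 2a". Separately, footnote e of the flowchart, attached to the row "Factor VIII Inhibitor in Plasma" at visits 1 and 2a, asks for the same gap before sampling: "Time from last treatment with current FVIII product should be at least 96 hours".

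**Bleeds.** Protocol 4.1.6: "Bleeds that occur during the screening and follow-up periods should be treated as per standard local practice and will not be assessed". Section 8.1.1 starts bleed recording at visit 2a.

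**Screen failures.** Protocol 5.4: "Minimal information includes demography, screen failure details, eligibility criteria, and laboratory results".

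**The concern.** Patients with severe haemophilia A are told to go without their current FVIII product for at least four days because the trial requires it. The obvious hazard is a bleed. This happens after consent, so it is part of trial participation, yet AE/SAE collection has not opened and bleeds in that period are not assessed. The sponsor's 24-hour rule applies to SAEs, and a pre-dose event is not an SAE under section 8.3.1. A serious event brought on by the interval would therefore not reach the sponsor by the expedited route and would not appear among the trial's safety events. The trial-procedures part of the risk table in section 2.3.1 covers injection, physical examination and COVID-19, but not this interval. What is at stake is oversight of a trial-imposed risk, not any efficacy or treatment-emergent estimate.

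**Working it through.** The plan states no figure on this point, so the check is mainly textual, with a small calculation for scale.

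**Step 1: is the interval after consent?** The flowchart puts consent at visit 1, about two weeks before visit 2a. The last 96 hours before visit 2a therefore fall after consent.

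**Step 2: does it apply to everyone?** Yes. Sections 6.5.1, 7.1 and 8.1.1 are not limited to the PK subgroup.

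**Step 3: where does a serious event in the interval go?**

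| Route | Open before first dose? | Source |
|---|---|---|
| AE/SAE form, 24-hour report | No | Protocol 8.3.1 |
| Bleed recording | No | Protocol 4.1.6, 8.1.1 |
| Treatment-emergent tables | No | SAP 5.4.2.2 |
| Bleeding endpoints | No; they count bleeds needing N8-GP | SAP 5.1 |
| Concomitant illness/medical history | Yes, without expedited reporting | Protocol 8.2, 8.3.1 |
| Screen-failure minimal data | Does not name medical history | Protocol 5.4 |

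The flowchart checks eligibility again at visit 2a, so a patient can go through the interval and then fail screening.

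**Step 4: would an earlier start date be enough?** Not for bleeds. Section 8.3.6 exempts bleeding episodes from standard AE/SAE reporting unless one of four conditions holds: greater intensity, frequency or duration than expected; a reasonable possibility of relation to the IMP; life-threatening; or fatal. Relation to the IMP cannot apply before the first dose. A bleed that led only to hospitalisation, and was not judged greater than expected for that patient, would stay exempt.

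**Step 5: scale.** Inputs are 36 planned patients (Protocol 1.1), 4 days (96 hours) and 28 weeks of treatment.
- FVIII-free time before visit 2a: 36 x 4 = 144 patient-days; 144 / 365.25 = 0.39 patient-years.
- Planned treatment time: 36 x 28 x 7 = 7,056 patient-days; 144 / 7,056 = 2.0%.

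The documents give no bleeding rate without FVIII. The only rate is a median ABR of 1.18 on N8-GP prophylaxis (Protocol 2.2), probably low for this purpose. Taking that, and assumed rates of 10 and 30 per year:
- 0.394 x 1.18 = 0.5 bleeds
- 0.394 x 10 = 3.9 bleeds
- 0.394 x 30 = 11.8 bleeds

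These are bleeds of any severity. Only serious ones judged related to the interval would be reportable, so the number of reports would be smaller.

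**The case against.** The best defence is that the start date follows from the protocol's own definition. Appendix 3 (10.3.1) ties an AE to use of the IMP, so collection from the first dose is coherent and deliberate. That stands, and it is why the remedy should leave the definition and the treatment-emergent window alone. It does not supply a reporting route for harm from a trial procedure before dosing, and no section does.

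Other limits also stand, and they rule out stronger readings that a reader might infer:

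- **That the interval before visit 1 counts equally.** It rests only on footnote e, and the flowchart places consent at visit 1. It counts only if consent was obtained before FVIII was withheld for that sample.
- **That such events leave no trace.** Medical history and the last coagulation-factor administration are recorded at visits 1 and 2a. Under 10.1.8.1, entered data become available to the sponsor, preferably within 5 working days. Section 10.3.1 also lets a condition first detected after dosing qualify as an AE. Section 5.4 sets a minimum for screen failures and does not forbid further data.
- **That the ethics committee would not learn of the event.** The investigator's duty in 10.1.1 covers SAEs or other significant safety findings as committee procedures require, and is not tied to the first dose.
- **That section 8.3.1 contradicts itself**, because it asks for SAEs related to trial participation after a patient has completed or been discontinued. That clause covers a different group at a different time.
- **That hours below 1% FVIII can be worked out.** Section 2.2 gives a 1.6-fold half-life ratio but no half-life for either product.

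**Conclusion.** The point holds in a narrow form. Between consent and first dose, the trial imposes an FVIII-free interval of at least 96 hours before visit 2a and provides no expedited sponsor-reporting route for serious harm that it causes. Such harm is recorded at most as concomitant illness or medical history, and possibly not at all for a patient who then fails screening.

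The time involved is at most 144 patient-days among included patients, taking 36 inclusions and a gap of exactly 96 hours that is wholly additional to usual care. It is less if some patients were treated on demand or at long intervals; the documents do not give that mix. Screen-failed patients would add an unknown amount. No endpoint, estimate or treatment-emergent table is biased. This is a cheap improvement in safety oversight, not a flaw in the analysis.

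One related conflict needs attention. Section 4.1.6 tells patients to keep to their normal regimen during screening and has screening bleeds treated by local practice, while sections 6.5.1 and 7.1 permit current FVIII only until 96 hours before visit 2a. These passages must be reconciled.

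**What to change.** - **Protocol 8.3.1:** from informed consent to first dose, require recording and 24-hour reporting of SAEs judged related to a trial-mandated procedure, naming the FVIII-free interval, for included and screen-failed patients.
- **Protocol 8.3.6:** state that a serious bleed judged related to that interval is reportable despite the disease-related-event exemption.
- **Protocol 4.1.6:** except such events from the statement that screening bleeds are not assessed, and reconcile this section with 6.5.1 and 7.1.
- **Protocol 5.4:** add these events to the minimal screen-failure data.
- **SAP 5.4.2.2:** list them separately, so that treatment-emergent summaries are unchanged.

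The cost is amended wording, a form opened at screening and a few extra pre-treatment reports.

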### 8.3.2 Method of detecting AEs and SAEs

The method of recording, evaluating, and assessing causality of AE and SAE and the procedures for completing and transmitting SAE reports are provided in [Appendix 3](#).

Care should be taken not to introduce bias when detecting AEs and/or SAEs. Open-ended and non-leading verbal questioning of the patient is the preferred method to inquire about events.

### 8.3.3 Follow-up of AEs and SAEs

After the initial AE/SAE report, the investigator is required to proactively follow each patient at subsequent visits/contacts. All SAEs should be followed until final outcome of the event or the patient is lost to follow-up as described in Section [7.3](#). Further information on follow-up and final outcome of events is given in [Appendix 3](#).

### 8.3.4 Regulatory reporting requirements for SAEs

Prompt notification by the investigator to Novo Nordisk or designee of a SAE is essential so that legal obligations and ethical responsibilities towards the safety of patients and the safety of a trial product under clinical investigation are met.

Novo Nordisk has a legal responsibility to notify both the local regulatory authority and other regulatory agencies about the safety of a trial product under clinical investigation. Novo Nordisk will comply with country-specific regulatory requirements relating to safety reporting to the regulatory authority, IRB/IEC, and investigators. This also includes suspected unexpected serious adverse reactions (SUSAR).

An investigator who receives an investigator safety report describing a SAE or other specific safety information (e.g. summary or listing of SAEs) from Novo Nordisk will review and then file it along with the investigator's brochure[17](#) and will notify the IRB/IEC, if appropriate according to local requirements.

